- To evaluate the superiority of romiplostim plus dexamethasone vs dexamethasone alone in terms of complete response (CR), response (R) global response (GR) and response within the target range (TR) at 6 months (Day 180), at 12 months (Day 365) from randomisation and at End of study Visit (visit 12 months after the last dose of study treatment). We will evaluate them in the total sample but also in a subgroup that excludes patients receiving any rescue treatment. Or an additional sensitivity analysis will be conducted to exclude patients receiving rescue treatment.
- To compare the time to first response defined as the time from randomization to first response (R) in both arms. We will evaluate this in the total sample and in the absence of any rescue treatment.

- To compare the proportion of patients with early response (ER) and initial response (IR) in both arms.
- To compare the duration of platelet response assessed as: the maximum number of consecutive days with platelet response (CR, R, GR and TR) and, the total number of days along the study period with platelet response (CR, R, GR and TR) in both arms. We will evaluate them in the total sample and in the absence of any rescue treatment.
- To compare the time to loss of response (LoR) in patients who achieved response in both arms.
- To compare the proportion of patients requiring any rescue treatment along the study period in both arms.
- To evaluate and compare proportion of treatment failure and time to treatment failure.
- To evaluate the safety and tolerability of study treatments in both arms.
- To compare the difference between study arms in the mean change in patients' bleeding
- To compare the change in patients' quality of life from baseline Day 1, (the day of administration of the first dose of study medication) toMonth2 (Week 8), Month 6 (Day 180), Month 12 (Day 365) and End of study Visit (visit 12 months after the last dose of study treatment) assessed SF-36v2, FACIT-F and ITP-PAQ in both arms.
- To describe and compare healthcare resources use (HRU) and loss of productivity in both study arms.

h. Study design

This is an open label, randomized, phase 3 study designed to compare romiplostim plus dexamethasone vs dexamethasone alone in terms of sustained response off any ITP treatment in adult subjects (≥18 years old) with newly diagnosed ITP.

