- To evaluate the superiority of romiplostim plus dexamethasone vs dexamethasone alone after 12 months (≥365 days) from treatment cessation, if data available, in patients with newly primary immune thrombocytopenia in terms of sustained response off any ITP treatment (12mSROT-30 and 12mSROT-50) from treatment cessation and without WHO grade 2 or more bleeding.
- To evaluate the superiority of romiplostim plus dexamethasone vs dexamethasone alone in terms of complete response (CR), response (R) global response (GR) and response within the target range (TR) at 6 months (Day 180), at 12 months (Day 365) from randomisation and End of study Visit (visit 12 months after the last dose of study treatment). We will evaluate them in the who trial cohort but also in a subgroup that excludes patients receiving any rescue treatment. Or an additional sensitivity analysis will exclude patients receiving rescue treatment.
- To compare the time to first response defined as the time from randomization to first response (R) in both arms. We will evaluate this in the total sample and in the absence of any rescue treatment.
- To compare the proportion of patients with early response (ER) and initial response (IR) in both arms.
- To compare the duration of platelet response assessed as: the maximum number of consecutive days with platelet response (CR, R, GR and TR) and, the total number of days along the study period with platelet response (CR, R, GR and TR) in both arms. We will evaluate them in the total sample and in the absence of any rescue treatment.
- To compare the time to loss of response (LoR) in patients who achieved response in both arms.
- To compare the proportion of patients requiring any rescue treatment along the study period in both arms

- To evaluate and compare proportion of treatment failure and time to treatment failure.
- To evaluate the safety and tolerability of study treatments in both arms.
- To compare the difference between study arms in the mean change in patients' bleeding
- To compare the change in patients' quality of life from baseline Day 1(the day of administration of the first dose of study medication) to 2 (Week 8), Month 6 (Day 180), Month 12 (Day 365) and End of study Visit (visit 12 months after the last dose of study treatment) assessed with SF-36 v2, FACIT-F and ITP-PAQ in both arms.
- To describe and compare healthcare resources use (HRU) and loss of productivity in both study arms.

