In the DEX arm, dexamethasone will be administered 40 mg daily x 4 days for up to 3 cycles every 14 to 28 days.

The use of commercial dexamethasone will be authorized up to 3 days, in case the patient is attended in emergency care while the criteria for the study are being checked and labeled study medication is assigned.

c. Treatment duration and monitoring

The monitoring will be the same in both arms with slight differences to allow for dose adjustments of romiplostim:

In the ROM + DEX arm patients will be reviewed weekly for 8 weeks (56 days). After Week 8, patients will be reviewed every 2 weeks (14 days) for 8 additional weeks and then monthly until Week 52 (Month 12) from randomization.

- o If romiplostim dose should be modified, patients will be reviewed weekly until a stable dose of romiplostim is reached for at least 4 weeks (28 days). After that, patients will go on with visits every 2 weeks (14 days) for 8 weeks and then monthly until Week 52(Month 12) from randomization.
- In the DEX arm, patients will be reviewed weekly until the completion of dexamethasone cycles and for a minimum of 8 weeks (56 days). After that, every 2 weeks (14 days) for 8 additional weeks and then monthly until Week 52 (Month 12) from randomization.

Once romiplostim or dexamethasone is stopped or after 365 days since randomization, patients should be clinically evaluated minimum every 4+/- 1 week for 12 months and continuation of treatment should be decided on an individual basis by the treating physician.

If patient needs treatment again it will be prescribed according to routine clinical practice. In case romiplostim is used, it will not be supported by the sponsor.

d. Criteria for dose adjustments

Dose adjustments for romiplostim will be based on platelet count as described in previous Dosage and administration section.

No dose adjustment for dexamethasone is permitted.

e. Rescue medication

We will consider rescue medication IVIg, platelet transfusion or prednisone. Tranexamic acid will be not considered rescue medication. Rescue medication will be used as follow:

- In the ROM + DEX arm, if platelets counts are lower than 20x10⁹/L or bleeding symptoms related to thrombocytopenia are present between romiplostim doses, rescue therapy with IVIg(maximum dose 2 gr/kg in total during 1 to 5 days) can be used. Prednisolone is not allowed in this arm.

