- In the DEX arm, if platelet counts are lower than 20x10⁹/L or bleeding symptoms related to thrombocytopenia are present between cycles, rescue therapy with IVIg (maximum dose 2 gr/kg in total during 1 to 5 days) or low doses of prednisone (0,5 mg/kg/d) can be used. If patients use rescue treatment with prednisone, they should be decreased as soon as possible and stopped within 8 weeks.

f. Treatment failure

In the ROM + DEX arm, it would be considered treatment failure if platelets are lower than 30x10⁹/L after 4 weeks with romiplostim at 10 mcg/kg/week or rescue

medication is needed to get this level of platelets despite this dose of 10mcg/kg/week for 4 weeks.

In DEX arm, it would be considered treatment failure if platelets are lower than 30x10⁹/L after 3 cycles of dexamethasone or if rescue medication is needed to get this level of platelets despite the 3 cycles of dexamethasone.

In both arms, treatment failure will be considered to in those patients bleeding who are refractory to therapy in whom it is considered clinically in their best interests to escalate or switch treatment in a way that does not align with the protocol treatment schedules. Patients will be discussed with Steering Committee before to be considered treatment failure.

If patients lose response on the DEX arm, they can be switched from one arm to the other (to TPO-RA), but outside the trial. The treatment will be provided by their centre and this information will be collected up in the CRF. The patients will be considered a treatment failure.

g. Accountability

The study medication (i.e., romiplostim, dexamethasone) will be sent directly from the sponsor to the investigator's site pharmacy preceded by the Regulatory Green Light. The medication is to be used exclusively in the clinical trial according to the instructions of this study protocol.

When a drug shipment is received, the Investigator or designee will check the amount and condition of the delivery, drug expiration date, and sign the Receipt of Shipment Form provided. The Receipt of Shipment Form should be faxed or sent by e-mail to the CRO. The original form will preliminarily be retained at the site and will be collected at the next monitoring visit by the monitor and stored in the TMF at CRO. A copy will remain in the Investigator File at the site. In case of shipment problems, the Investigator or designee shall contact the CRA as soon as possible.

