- To compare the time to first response (R) in both arms, Kaplan-Meier method will be used. Patients who not achieve R will be censored at the date of the last followup. Median and 95% CI, number of events and censored and risk number of patients will be provided. Log rank test will be used to compare time to first response between treatment arms. We will evaluate this in the total sample and in the absence of any rescue treatment.
- The proportion of patients with ER at Day 7 and IR at Day 30 from randomisation will be calculated and corresponding 95% CIs for each study arm will be provided.
 A Chi- square test or Fisher test if applicable will be used to compare the proportion of each endpoint between treatment arms.
- Descriptive statistics (mean, median, standard deviation, min, max, Q1 and Q3) and Student's t test will be used to compare the duration of platelet response through the following endpoints:
 - maximum number of consecutive days with platelet response (CR, R, GR and TR) along the study period and,
 - total number of days with platelet response (CR, R, GR and TR) along the study period in both arms. We will evaluate them in the total sample and in the absence of any rescue treatment.
- To compare the time to loss of response (LoR) in the subgroup of patients who achieve R (rITT population) between both arms, Kaplan-Meier method will be used. Patients who do not achieve LoR will be censored at the date of the last follow-up. Median and 95% CI, number of events and censored and risk number of patients will be provided. Log rank test will be used to compare time to first response between treatment arms.

 The proportion of patients requiring any rescue treatment along the study period will be calculated and corresponding 95% CIs for each study arm will be provided.
 A Chi-square test or Fisher test if applicable, will be used to compare the proportion between treatment arms.

Frequency and proportion of patients with adverse events, including bleeding events measured by the WHO bleeding scale will be provided. A Chi-square test or Fisher test if applicable will be used to compare the proportion between treatment arms.

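### Comparing CR, R, GR and TR after excluding rescued patients breaks the randomised comparison; keep everyone and count prior rescue as non-response

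*Protocol*

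**What the plan says.** The secondary objectives (Protocol, sections 1.g and 5.c) compare CR, R, GR and TR between arms at Day 180, Day 365 and the End of study Visit. Section 1.g says: "We will evaluate them in the total sample but also in a subgroup that excludes patients receiving any rescue treatment". It then adds "Or an additional sensitivity analysis will be conducted to exclude patients receiving rescue treatment". Section 5.c has the same pair of sentences: "but also in a subgroup that excludes patients receiving any rescue treatment. Or an additional sensitivity analysis will exclude patients receiving rescue treatment". The text does not settle whether this is a subgroup or a sensitivity analysis, but both options drop rescued patients.

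Elsewhere the wording differs. The endpoint lists (1.j and 6.c) and the time-to-first-response bullet in 11.e use the form "We will evaluate this in the total sample and in the absence of any rescue treatment", which does not say what happens to a rescued patient. The 11.e bullet for CR, R, GR and TR mentions no rescue-free analysis.

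Section 9.e lists IVIg, platelet transfusion and prednisone as rescue. In ROM+DEX the trigger is a platelet count below 20x10⁹/L, or "bleeding symptoms related to thrombocytopenia are present between romiplostim doses, rescue therapy with IVIg"; "Prednisolone is not allowed in this arm". In DEX the count threshold is the same, or "bleeding symptoms related to thrombocytopenia are present between cycles, rescue therapy with IVIg", and low-dose prednisone is also permitted. Need for rescue is itself a secondary endpoint compared between arms. Section 11.c makes the mITT population, analysed as randomised, the primary efficacy set.

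**The concern.** Rescue is a consequence of how the patient is doing on the assigned treatment. Removing rescued patients conditions on an outcome, so the remaining groups need not be alike in prognosis even though the randomised groups were.

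Three features make unequal removal plausible:
- The rescue window runs between romiplostim doses for up to 12 months in one arm, and between at most three dexamethasone cycles in the other.
- The permitted agents differ by arm.
- The trial is open label, and its rationale (5.b) expects the combination to reduce the need for rescue.

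The exclusion also covers *any* rescue, without a time limit. A ROM+DEX patient in response at Day 180 and first rescued in Month 9 would be taken out of the Day 180 comparison because of a later event.

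At stake is the answer to a reasonable question: does the combination give more response without rescue? The excluded-patient analysis does not answer it, although the objective is worded as superiority.

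**Working it through.** **The plan's own figure.** The rescue-excluding analysis has none. The stated sample size is used here only for scale, and it reproduces. With 30% versus 56.6%, two-sided 5%, 80% power and pooled variance: n = [1.960 × √(2 × 0.433 × 0.567) + 0.842 × √(0.30 × 0.70 + 0.566 × 0.434)]² / 0.266² = 53.3, so 54 per arm. For 15% dropout, 54 × 1.15 = 62.1, rounded up to 63; 54 / 0.85 = 63.5, rounded up to 64. The protocol states 63.

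**Formula.** Let p be the response rate among all patients in an arm, r the share rescued, and q the response rate among the rescued. The rate after exclusion is (p − r·q) / (1 − r). With rescue counted as non-response it is p − r·q, on all patients.

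**Inputs.** 63 per arm is from section 11.b. The rates 30% and 56.6% are borrowed from the primary endpoint, which is a different endpoint. The 40% rate, all rescue rates and q are assumptions.

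**Example.** p = 40% in both arms, r = 40% (DEX) and 20% (ROM+DEX), q = 0:
- DEX: 0.40 / 0.60 = 66.7%, on 63 × 0.60, about 38 patients.
- ROM+DEX: 0.40 / 0.80 = 50.0%, on 63 × 0.80, about 50 patients.
- Counting rescue as non-response instead: 40% versus 40%, on 63 per arm.

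**Range.** Differences are ROM+DEX minus DEX. The last column is the approximate chance of p<0.05 in a two-sided test of proportions.

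| True rates, DEX / ROM+DEX | Rescued, DEX / ROM+DEX | q | After exclusion | Difference (true) | Chance of p<0.05 |
|---|---|---|---|---|---|
| 40% / 40% | 20% / 20% | 0 | 50.0% / 50.0% | 0 (0) | 5% |
| 40% / 40% | 30% / 10% | 0 | 57.1% / 44.4% | −12.7 (0) | 24% |
| 40% / 40% | 40% / 20% | 0 | 66.7% / 50.0% | −16.7 (0) | 34% |
| 40% / 40% | 40% / 20% | 20% | 53.3% / 45.0% | −8.3 (0) | 12% |
| 40% / 40% | 20% / 40% | 0 | 50.0% / 66.7% | +16.7 (0) | 34% |
| 30% / 56.6% | 30% / 10% | 0 | 42.9% / 62.9% | +20.0 (+26.6) | 52% |
| 30% / 56.6% | 50% / 10% | 0 | 60.0% / 62.9% | +2.9 (+26.6) | 6% |
| 30% / 56.6% | 20% / 40% | 0 | 37.5% / 94.3% | +56.8 (+26.6) | near 100% |
| 30% / 56.6% | 20% / 20% | 0 | 37.5% / 70.7% | +33.2 (+26.6) | 93% |

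Equal rescue removes the distortion only when the true rates are also equal; the last row still inflates the difference. In the fourth row, response without rescue is 0.40 − 0.40 × 0.20 = 32% in DEX and 0.40 − 0.20 × 0.20 = 36% in ROM+DEX. That is 4 points in favour of ROM+DEX, while exclusion shows 8.3 points against it.

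**The case against.** The strongest reply is that little depends on this analysis. The total-sample comparison is kept, section 11.e calls secondary results exploratory, and rescue use is compared between arms, so an imbalance would be seen. The primary endpoint and the other SROT endpoints have absence of rescue in their definitions and are untouched. All of this stands, and it limits the weight of the point. It does not make the excluded-patient comparison interpretable.

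A reader might infer more than the protocol supports:
- *That rescued patients are also excluded for time to first response and days in response.* Exclusion is stated only for CR, R, GR and TR. For the other endpoints the wording is open. Sections 1.j and 6.c place absence of rescue inside the definition of time to first response, which can be read as the composite rule proposed here. The need there is clarification.
- *That the exclusion removes treatment failures, and more of them from one arm.* No rescue rates are given, so unequal removal is an inference. Rescue and failure overlap but differ: under 9.f, rescue counts as failure only when needed despite four weeks at the maximum romiplostim dose or despite three dexamethasone cycles.
- *That the plan favours ROM+DEX.* If rescue is commoner in DEX, as the rationale expects, the distortion would usually work against ROM+DEX.
- *That IVIg is the only rescue in ROM+DEX.* Section 9.e also lists platelet transfusion, without restriction by arm.
- *That the total-sample version is wrong.* It compares response whatever rescue was given, which is a legitimate question.

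**Conclusion.** The point holds for CR, R, GR and TR. Sections 1.g and 5.c state a rule that selects patients on a post-randomisation, outcome-driven event, and the *Or* sentence does not avoid it. This is a rule fixed badly, not a detail left for the analysis plan.

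Its size cannot be derived from the protocol. Under the assumed rescue rates of 10% to 50%, the distortion runs from none to tens of percentage points and can take either sign. It shrinks as more rescued patients respond. The consequence is moderate to low, because the affected analyses are supplementary and exploratory and the primary conclusion does not depend on them. The correction is cheap and worth making before database lock.

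**What to change.** 1. In 1.g and 5.c, replace the exclusion and *Or* sentences with a rescue-free analysis on the full mITT population: a patient rescued before the assessed time point is a non-responder at that time point. Keep the total-sample analysis. This follows the SROT convention already in the protocol.
2. In 1.j, 6.c and 11.e, state that absence of rescue means the same rule for time to first response and days in response. Patients are kept, rescue before response means no response, and days from first rescue onward are not response days. Add the rescue-free analysis to the CR, R, GR and TR bullet in 11.e.
3. Apply the rule also to off-protocol ITP therapy. Under 9.f a DEX patient may switch to a TPO-RA outside the trial and is then a treatment failure, but a TPO-RA is not rescue under 9.e. Without this addition, such a patient could count as a rescue-free responder.
4. Confirm that dates of rescue and other ITP treatment are recorded through the End of study Visit. In Table 3 the rescue-medication row has no mark for Visits 26–37. Concomitant medication continues to be recorded, and 9.h asks for its start and stop dates, but 9.h says only that rescue will also be collected.

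The cost is wording, some programming and a check of the eCRF, with no change to treatment or sample size. The downside is lower absolute response rates. A patient rescued early who later responds unaided also counts as a non-responder in this analysis; the retained total-sample analysis still shows that response.

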3. ABBREVIATIONS

Abbreviation	Full terminology
6mSROT-30	SROT with platelets higher or equal than 30x10 ⁹ /L for 6 months
6mSROT-50	SROT with platelets higher or equal than 50x10 ⁹ /L for 6 months
12mSROT-30	SROT with platelets higher or equal than 30x10 ⁹ /L for 12 months
12mSROT-50	SROT with platelets higher or equal than 50x10 ⁹ /L for 12 months
AE	Adverse Event
AESI	Adverse Event of Special Interest
ALT	Alanine aminotransferase
ASH	American Society for Hematology
AST	Aspartate aminotransferase
СВС	Complete Blood Counts
CI	Confidence Interval
СР	Complete Response
СРК	Creatinine Phosphokinase
CR	Complete Response
CRF	Case Report Form
CRA	Clinical Research Associate
CRO	Clinical Research Organization
CSR	Clinical Study Report
CTCAE	Common Terminology Criteria for Adverse Events
DEX	Dexamethasone

Abbreviation	Full terminology
ECG	Electrocardiogram
eCRF	Electronic Case Report Form
EDC	Electronic Data Capture
EOS	End Of Study
EOT	End of Treatment
EQ-5D-5L	5-level European Quality of Life–5 Dimensions
ER	Early Response
еТРО	Endogenous Thrombopoietin
FSH	Follicle-Stimulating Hormone
GCP	Good Clinical Practice
GGT	Gamma-Glutamyl Transferase
GR	Global Response
HBV	Hepatitis B Virus
HIV	Human Immunodeficiency Virus
HRU	Health Resource Utilization
ICF	Informed Consent Form
ICH	International Council for Harmonisation
IEC	Independent Ethics Committee
IVIg	Intravenous Immunoglobulin
IgM	Immunoglobulin M
INR	International Normalized Ratio
IP	Investigational Product
IR	Initial Response

Abbreviation	Full terminology
IRB	Institutional Review Board
ITP	Immune Thrombocytopenia
ITP-BAT	Immune Thrombocytopenia - Bleeding Assessment Tool
IUD	Intrauterine device
IUS	Intrauterine hormonal-releasing system
IV	Intravenous
K	Potassium
Kg	Kilogram
L	Liter
LDH	Lactate Dehydrogenase
LoR	Loss of Response
MedDRA	Medical Dictionary for Regulatory Activities
Mg	Milligram
Mcg	Microgram
mM	Micromolar
Na	Sodium
NASH	Nonalcoholic Steatohepatitis
PR	Partial Response
QC	Quality Control
R	Response
rHU	Recombinant Human
rHuTPO	Recombinant human anti-thrombopoietin
ROM	Romiplostim

Abbreviation	Full terminology
S	Skin
SC	Subcutaneous
SAE	Serious Adverse Event
SD	Standard Deviation
SMOG	Gradation of Severity
SOC	Standard of Care
SOP	Standard Operating Procedures
SR	Sustained Response
SROT	Sustained Response Off any ITP Treatment
TBL	Total Bilirubin
ТВС	To Be Concrete
TPO	Thrombopoietin
TR	Response within the Target Range
ULN	Upper Limit of Normal
WHO	World Health Organisation

4. CLINICAL TRIAL CHARACTERISTICS

a. Clinical trial identification

Code: RODEX

Title: A multicentre, randomized, open-label study of romiplostim plus dexamethasone vs dexamethasone in patients with newly diagnosed primary immune thrombocytopenia.

b. Phase

Phase III

c. Investigational product

Romiplostim and dexamethasone

d. Sponsor

Sponsor

Fundación Pública Andaluza para la Gestión de la Investigación en Salud de Sevilla (FISEVI)

Hospital Universitario Virgen del Rocío [name] [name] [name]

[contact]

Coordinating Investigator

[name]
Hospital Universitario Virgen del Rocío
Haematology Department
[name]
[name]

[contact]

e-mail: [contact]

Medical Monitor

[name] [name] Hospital Universitario Virgen del Rocío [name] [name] [name]

[contact]

e. Ethics Committee

SPAIN: Comité de Ética de la Investigación con medicamentos Provincial de Sevilla.

ITALY: Comitato Etico dell'Università "Sapienza"

UNITED KINGDOM: Wales Research Ethics Committee 1 Cardiff (REC

number: 23/WA/0199).

f. Study calendar

First patient inclusion: Last quarter 2022

Last patient inclusion: First quarter 2024

Subject participation duration: 18 months

Study duration: 24 months

